9.1 Definitions

Unanticipated Problems Involving Risk to Subjects or Others:

Any incident, experience, or outcome that meets all of the following criteria:

- Unexpected in nature, severity, or frequency (i.e. not described in study-related documents such as the IRB-approved protocol or consent form, the investigators brochure, etc.)

CONFIDENTIAL

This material is the property of the University of Pennsylvania. Do not disclose or use except as authorized in writing by the study sponsor

- Related or possibly related to participation in the research (i.e. possibly related means there is a reasonable possibility that the incident, experience, or outcome may have been caused by the procedures involved in the research)
- Suggests that the research places subjects or others at greater risk of harm (including physical, psychological, economic, or social harm).

Adverse Event:

An **adverse event** (AE) is any symptom, sign, illness or experience that develops or worsens in severity during the course of the study (regardless if study-related). Intercurrent illnesses or injuries should be regarded as adverse events. Abnormal results of diagnostic procedures are considered to be adverse events if the abnormality:

- results in study withdrawal
- is associated with a serious adverse event
- is associated with clinical signs or symptoms
- leads to additional treatment or to further diagnostic tests
- is considered by the investigator to be of clinical significance

Serious Adverse Event:

Adverse events are classified as serious or non-serious. A **serious adverse event** (SAE) is any AE that is:

- fatal
- life-threatening
- requires or prolongs hospital stay
- results in persistent or significant disability or incapacity
- a congenital anomaly or birth defect
- an important medical event

Important medical events are those that may not be immediately life threatening, but are clearly of major clinical significance. They may jeopardize the subject, and may require intervention to prevent one of the other serious outcomes noted above. For example, drug overdose or abuse, a seizure that did not result in in-patient hospitalization, or intensive treatment of bronchospasm in an emergency department would typically be considered serious.

All adverse events that do not meet any of the criteria for serious should be regarded as **non-serious adverse events**.

Adverse Event Reporting Period:

The study period during which AEs/SAEs will be reported is from the initiation of any study procedures until the end of the study. Any event(s) that the subject, or the subject's personal physician, believes might reasonably be related to participation in the study after the final time point will be assessed and reported as appropriate.

Preexisting Condition:

A preexisting condition is one that is present at the start of the study. A preexisting condition should be recorded as an adverse event if the frequency, intensity, or the character of the condition worsens during the study period.

Post-study Adverse Event:

All unresolved adverse events should be followed by the investigator until the events are resolved, the subject is lost to follow-up, or the adverse event is otherwise explained. At the last scheduled visit, the investigator should instruct each subject to report any subsequent event(s) that the subject, or the subject's personal physician, believes might reasonably be related to participation in this study.

CONFIDENTIAL

This material is the property of the University of Pennsylvania. Do not disclose or use except as authorized in writing by the study sponsor

Hospitalization, Prolonged Hospitalization or Surgery:

Any AE that results in hospitalization or prolonged hospitalization should be documented and reported as a SAE unless specifically instructed otherwise in this protocol. Any condition responsible for surgery should be documented as an AE if the condition meets the criteria for an AE.

Neither the condition, hospitalization, prolonged hospitalization, nor surgery are reported as an adverse event in the following circumstances:

- Hospitalization or prolonged hospitalization for diagnostic or elective surgical procedures for a preexisting condition. Surgery should **not** be reported as an outcome of an adverse event if the purpose of the surgery was elective or diagnostic and the outcome was uneventful.
- Hospitalization or prolonged hospitalization required to allow efficacy measurement for the study.
- Hospitalization or prolonged hospitalization for therapy of the target disease of the study, unless it is a worsening or increase in frequency of hospital admissions as judged by the clinical investigator.

9.2 Collection and Recording of Adverse Events

9.2.1 AE Collection Methods

All AEs and SAEs occurring during the study period will be captured through the methods described below:

1. Open-Ended AE Form: Participants will be asked an open-ended question about any symptom or medical event that may be related to their study participation. These events will be documented as **unanticipated (unexpected)** AEs unless they are otherwise outlined in the protocol or consent (i.e. related to withdrawal, assessments, etc.). The reporting period for each assessment will inquire about any event(s) or symptom(s) experienced since the last in-person visit. If a participant reports a symptom or medical event, they will be asked to rate the severity of the event utilizing the following severity scale: 0 (None=No Concerns), 1 (Mild=Issue does not interfere with usual daily activities), 2 (Moderate=Issue does interfere with some activities), and 3 (Severe=No normal activities are possible). Any report on the Open-Ended AE Form will require additional follow up per the AE documentation and internal reporting procedures outlined below in section 8.2.2.
2. Spontaneous Assessment: Once enrolled, participants will be instructed to inform the research team about any notable symptom or medical event/concern throughout their participation in the study. A participant may also request the Principal Investigator be consulted about any reported medical event or concern of any severity at any time throughout their participation.
3. An “AE Note” template will be available to the research staff to collect supporting AE information and will function as the source document. However, research staff may collect AE information on any source document available to them and transfer the relevant information to a formal AE Note at a later time. Any notable AE reported spontaneously will require additional follow up per the AE documentation and internal reporting procedures outlined below in section 8.2.2.

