Breath Alcohol Concentration (BrAC): Participants will complete a BrAC assessment at Laboratory Visit 1. Participants will be made aware of the BrAC assessment prior to the visit and asked to avoid alcohol and alcohol-based products (e.g. mouthwash, breath spray, etc.) the evening and morning before Laboratory Visit 1. The BrAC monitor is a handheld device that uses a disposable mouthpiece and reports the concentration of alcohol in exhaled breath. Any reading greater than 0.000 indicates alcohol consumption within the last 14 hours. Participants with a BrAC greater than 0.000 at Laboratory Visit 1 will be deemed ineligible.

Medical History Form: A medical history form (led by the research staff) will be completed to review for applicable contraindications previously listed under Key Inclusion/Exclusion Criteria at Laboratory Visit 1.

Demographics and Smoking History: Standard surveys will collect demographics information such as age, sex, race, ethnicity, education level, and income. Standard survey questions will assess cigarillo use history (number and flavored), use of other combustible products, as well as cigarette smoking history (e.g., age at initiation, current smoking rate). Nicotine dependence will be assessed with the Fagerstrom Test for Nicotine Dependence (FTND). This 6-item measure has good internal consistency ($\alpha = .64$) and high test-retest reliability. Nicotine dependence will also be assessed using the Hooked on Nicotine Checklist (HONC).

Adverse Events Form (Open-Ended AEs): Participants will be asked an open-ended question about any symptom or medical event that may be related to their study participation. These events will be documented as **unanticipated (unexpected) AEs** unless they are otherwise outlined in the protocol and/or consent form (i.e. related to withdrawal, assessments, etc.). The reporting period for each assessment will inquire about any event(s) or symptom(s) experienced since the last in-person visit. If a participant reports a symptom or medical event, they will be asked to rate the severity of the

CONFIDENTIAL

This material is the property of the University of Pennsylvania. Do not disclose or use except as authorized in writing by the study sponsor

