9.2.2 AE/SAE Documentation and Internal Reporting Procedures

CONFIDENTIAL

This material is the property of the University of Pennsylvania. Do not disclose or use except as authorized in writing by the study sponsor

AE/SAE Documentation: At a minimum, follow-up information will include AE/SAE onset/resolution, description of event/course, severity, action taken, outcome, and possible relation to study participation.

Information surrounding AEs and SAEs will be initially recorded on the appropriate source document such as the SEC Form, an “AE Note” or SAE Form, and/or any document in which the AE/SAE information was originally recorded. All applicable AEs and SAEs will then be documented on a cumulative AE and SAE log maintained within the regulatory binder.

Completed documentation of applicable AEs will include the following information:

- Protocol Title and IRB#
- Subject Identifier
- Event Title
- Date Site Notified
- Event Start Date and Time
- Event Stop Date and Time
- Description of Event/Course (including sequelae)
- Severity:
 - None = No concerns
 - Mild = Side effect or issue does not interfere with usual daily activities
 - Moderate = Side effect or issue interferes with some activities
 - Severe = No normal activities are possible
- Relatedness to the study procedures (PI):
 - Unrelated = Definitely not related
 - Unlikely = Doubtfully related
 - Possibly = May be related
 - Probably = Likely related
 - Definitely = Related
- Expectedness per protocol and/or consent
 - Expected/Anticipated
 - Unexpected/Unanticipated
- Action(s) taken (if appropriate)
- Outcome (if appropriate)

Documentation of SAEs will include the following information on a standardized SAE Form:

- Protocol name and number
- Subject identifiers
- Demographic data
- Date Site Notified
- Date and time of SAE onset
- Date and time of SAE resolution, if available
- Course/Description of Event (including sequelae)
- Action Taken
- Outcome
- Follow-up plan

CONFIDENTIAL

This material is the property of the University of Pennsylvania. Do not disclose or use except as authorized in writing by the study sponsor

- Serious Status (What makes the event an SAE)
- Severity of the event
 - None = No concerns
 - Mild = Side effect or issue does not interfere with usual daily activities
 - Moderate = Side effect or issue interferes with some activities
 - Severe = No normal activities are possible
- Relatedness to the study procedures (PI):
 - Unrelated = Definitely not related

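### The only scheduled adverse event question is limited to possibly related events, although the protocol defines adverse events regardless of relatedness and says its methods together capture them all

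*Combined protocol and SAP*

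**What the plan says.** Section 9.1 of the protocol defines an AE broadly. It is something that "develops or worsens in severity during the course of the study (regardless if study-related"), and the definition adds: "Intercurrent illnesses or injuries should be regarded as adverse events".

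Section 9.2.1 opens with a statement of completeness: "All AEs and SAEs occurring during the study period will be captured through the methods described below". Three items follow:

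- **Open-Ended AE Form.** Participants are asked about "any symptom or medical event that may be related to their study participation". Section 7.4.1 repeats this: they are "asked an open-ended question about any symptom or medical event that may be related to their study participation". Further on, the same item says: "The reporting period for each assessment will inquire about any event(s) or symptom(s) experienced since the last in-person visit".
- **Spontaneous Assessment.** Enrolled participants are told to inform staff of notable symptoms, events or concerns. No relatedness condition is attached.
- **AE Note.** This is a template on which staff record information about an event.

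Sections 7.2.2 to 7.2.4 schedule the Open-Ended AE Form at each of the three laboratory visits. Section 9.2.2 then has each event graded for "Relatedness to the study procedures (PI") on five levels, the lowest being definitely not related.

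**The concern.** The definition and the question have different scopes. The definition disregards relatedness, while the opening description of the question makes possible relatedness a condition of being asked. Someone who had a cold, an injury or a spell of dizziness and put it down to something else could truthfully answer no, although each of these is an AE under 9.1 if it arose during the study.

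Two things are at stake. One is whether the AE record is as complete as 9.2.1 says it will be. The other is the order of judgment. Section 9.2.2 gives the relatedness grade to the investigator, but the investigator can grade only what is reported. If participants screen first, the lower grades will tend to be under-filled. An event that a participant wrongly dismisses also never reaches the investigator's assessment of relatedness and expectedness, on which expedited reporting to the IRB depends (9.3.2).

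**Working it through.** No arithmetic applies, and the plan gives no figure to reproduce. The check is to take each kind of event that is an AE under 9.1 and ask which described method would reach it.

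| Event, as the participant sees it | AE under 9.1? | Form, opening sentence | Form, recall-period sentence | Spontaneous Assessment |
|---|---|---|---|---|
| Possibly related, notable | Yes | Asked | Asked | Covered if volunteered |
| Possibly related, not notable | Yes | Asked | Asked | Not covered |
| Unrelated, notable | Yes | Not asked | Asked | Covered if volunteered |
| Unrelated, not notable | Yes | Not asked | Asked | Not covered |

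1. On the opening sentence, rows 3 and 4 are not solicited. Row 3 is left to unprompted report, and row 4 is reached by neither method.
2. On the recall-period sentence taken alone, all four rows are solicited. The item therefore supports two readings. The restrictive one describes the question itself and appears in both 7.4.1 and 9.2.1. The wider one appears in a sentence whose evident purpose is to set the time window.
3. The AE Note does not change the table, because it records events and does not ask about them.
4. Section 9.1 shows which scope was intended during the study. Its reporting-period paragraph covers AEs and SAEs from the first procedure to the end of the study with no relatedness condition. It brings in a condition, that the subject or the subject's physician believes the event might reasonably be related, only for events after the final time point. The form's opening sentence applies a similar condition during the study itself.
5. The grading scale in 9.2.2 points the same way. A category for definitely unrelated events presupposes that such events are in the record.

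The share of AEs lost would be the share that participants regard as unrelated, multiplied by the share of those not volunteered. The documents give neither factor, so no estimate follows.

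**The case against.** The strongest reply is that the protocol does not rely on the form alone. A reader might infer that the form by itself is said to capture all AEs. It is not: 9.2.1 attributes completeness to the methods together, and Spontaneous Assessment is an instructed method without a relatedness limit. The recall-period sentence also refers to any event, and the form itself is not reproduced, so the exact question put to participants cannot be established. These points stand and narrow the gap. They do not close it: spontaneous report is unsolicited and limited to notable events, and an item that can be read two ways is itself a reason to settle the wording.

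A reader might also infer that causality assessment passes from the investigator to the participant. That goes too far. The investigator grades every reported event, and the participant's threshold is only that a link is possible. What remains is a pre-screen at a low threshold.

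Nor do the documents support an inference that cigarillo reactions will go unnoticed. Section 8.1 names nausea, dizziness and rapid heartbeat, and the consent form tells participants they may report these at once. Study cigarillos are smoked only in the laboratory, and the Visit 3 session is observed (4.5). The medication reviews at Visits 2 and 3 could also bring a treated illness to light, though only indirectly.

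Finally, no planned result uses these data. Section 7.5 contains no AE analysis. Expedited IRB reporting of AEs requires an event to be unexpected and probably or definitely related (9.3.2). Section 8.3.1 does require all SAEs to go to the IRB, but serious events would ordinarily be notable. This limits the consequence without removing the inconsistency.

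Section 9.2.2 also names an SEC Form that 9.2.1 and the visit procedures do not describe. Whether it would help cannot be determined.

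**Conclusion.** Wrong as written: the collection rule is inconsistent with the protocol's own AE definition. The gap is specific. Events that participants see as unrelated depend on unprompted report, and those that are also not notable are not assured of capture by any described method. The statement that all AEs and SAEs will be captured is not supported for that group.

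The conclusion assumes that the form's question follows its description in 7.4.1 and 9.2.1, and that the participant decides what may be related. The second is a natural inference, since the question is put to the participant, but it is not the protocol's wording.

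A reader might go on to infer a known downward bias in an AE rate. The documents do not support one, because they neither give the inputs nor plan such a rate. The likely effect is on the completeness of the AE record and its mix of relatedness grades. The three primary outcomes are unaffected.

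**What to change.** In 7.4.1 and 9.2.1, reword the form's question to cover *any symptom, illness or medical event since the last visit, whether or not you think it is related to the study*. This matches the definition in 9.1 and the recall-period sentence already in the item. Leave relatedness to the investigator, as 9.2.2 provides. Check that the form in use carries the same wording.

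The cost is one reworded question and a few more unrelated events to log and grade.

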9.2.2 AE/SAE Documentation and Internal Reporting Procedures

CONFIDENTIAL

This material is the property of the University of Pennsylvania. Do not disclose or use except as authorized in writing by the study sponsor

AE/SAE Documentation: At a minimum, follow-up information will include AE/SAE onset/resolution, description of event/course, severity, action taken, outcome, and possible relation to study participation.

Information surrounding AEs and SAEs will be initially recorded on the appropriate source document such as the SEC Form, an “AE Note” or SAE Form, and/or any document in which the AE/SAE information was originally recorded. All applicable AEs and SAEs will then be documented on a cumulative AE and SAE log maintained within the regulatory binder.

Completed documentation of applicable AEs will include the following information:

- Protocol Title and IRB#
- Subject Identifier
- Event Title
- Date Site Notified
- Event Start Date and Time
- Event Stop Date and Time
- Description of Event/Course (including sequelae)
- Severity:
 - None = No concerns
 - Mild = Side effect or issue does not interfere with usual daily activities
 - Moderate = Side effect or issue interferes with some activities
 - Severe = No normal activities are possible
- Relatedness to the study procedures (PI):
 - Unrelated = Definitely not related
 - Unlikely = Doubtfully related
 - Possibly = May be related
 - Probably = Likely related
 - Definitely = Related
- Expectedness per protocol and/or consent
 - Expected/Anticipated
 - Unexpected/Unanticipated
- Action(s) taken (if appropriate)
- Outcome (if appropriate)

Documentation of SAEs will include the following information on a standardized SAE Form:

- Protocol name and number
- Subject identifiers
- Demographic data
- Date Site Notified
- Date and time of SAE onset
- Date and time of SAE resolution, if available
- Course/Description of Event (including sequelae)
- Action Taken
- Outcome
- Follow-up plan

CONFIDENTIAL

This material is the property of the University of Pennsylvania. Do not disclose or use except as authorized in writing by the study sponsor

- Serious Status (What makes the event an SAE)
- Severity of the event
 - None = No concerns
 - Mild = Side effect or issue does not interfere with usual daily activities
 - Moderate = Side effect or issue interferes with some activities
 - Severe = No normal activities are possible
- Relatedness to the study procedures (PI):
 - Unrelated = Definitely not related
 - Unlikely = Doubtfully related
 - Possibly = May be related
 - Probably = Likely related
 - Definitely = Related
- Clinical assessment of subject conducted at time of SAE (if appropriate)
- Results of any laboratory tests and/or diagnostic procedures (if appropriate)
- Autopsy findings (if appropriate)
- Concomitant medications and therapies (excluding treatment of event)
- Relevant Medical History (if appropriate)

Internal Reporting Procedures: All relevant follow-up information outlined above (see AE/SAE documentation) concerning applicable AEs, including all information regarding the occurrence of previously reported event(s), will be reported to the Study Coordinator (or other senior personnel) and Principal Investigator to determine a course of action (e.g. continue to monitor), relatedness (causality) to the study, and expectedness (if not already established). This consult will be documented via email. The clinical course of each event will be followed until resolution, stabilization, or until it has been determined that the study treatment or participation is not (or unlikely) to be the cause.

SAEs that are still ongoing at the end of the study period must be followed up to determine the final outcome unless it has been determined that the study treatment or participation is not the cause. Any SAE that occurs after the study period and is considered to be possibly related to the study treatment or study participation should be recorded and reported immediately per this protocol.

9.3 Reporting of Serious Adverse Events and Unanticipated Problems

The reporting requirements of applicable SAEs and/or Unanticipated Problems including reportable AEs (see section 8.1 for definitions) to external entities are detailed in the following sub-sections:

9.3.1 Investigator reporting: notifying NIDA and FDA

The following events/reports will be submitted to the FDA and NIDA Project/Program Officer in a narrative format or on FDA Form 3500A:

- Unexpected fatal or life-threatening suspected adverse reactions (in relation to study-provided cigarillos) will be reported as soon as possible, but in no case later than 7 calendar days after the initial receipt of the information.

